5.4 Adjustments for Covariates

N/A

5.5 Handling of Dropouts or Missing Data

Any missing values at dialysis treatment level of an endpoint will not be imputed.

If a subject missed a HD treatment but was able to have an unplanned HD treatment with the same requirements, the results from the unplanned HD treatment will replace the missed one.

5.6 Interim Analyses

No interim analysis is planned.

5.7 Multicenter Studies

One to two study sites were planned as stated in the protocol. One site enrolled subjects for the study.

5.8 Multiple Comparisons/Multiplicity

N/A

5.9 Use of an "Efficacy Subset" of Subjects

N/A

5.10 Active-Control Studies Intended to Show Equivalence/Non-inferiority

N/A

5.11 Examination of Subgroups

Version 2.0 6/30/2021 Page 7 of 13

Due to small numbers of subjects in the study, subgroup analyses were not performed.

6 STATISTICAL ANALYSES

6.1 Patient Disposition

The subject disposition table will include the items below:

- The number of subjects who signed the informed consent and were screened.
- The number of subjects who failed screening with reasons.
- The number of subjects who were eligible.
- The number of subjects who were randomized.
- The numbers of subjects who completed the following stages: Period 1, Washout, Period 2, and end of study.
- The number of subjects and percent by category of major reasons for early discontinuation.
- The numbers of subjects in the safety and in the analysis populations.

Subject inclusion in the different analysis sets will be listed for all subjects. Subject disposition data will be presented in a listing for all subjects.

6.2 Protocol Deviations

Any protocol deviation will be listed. Summaries by category of protocol deviations will be presented if the number of protocol deviations is sufficiently large.

6.3 Demographic and Other Baseline Characteristics

- Demographic characteristics: descriptive statistics will be presented for age, frequency, and percent will be presented for sex, race, and ethnicity.
- Dialysis history: frequency, and percent of primary cause of ESRD, and current vascular access will be presented. In addition, descriptive statistics for dialysis vintage will be presented.
- Medical history: all medical history and non-pharmacological treatment/therapies recorded will be listed for each subject.
- Initial HD prescriptions and any prescription changes other than heparin dose and bloodline will be listed for each subject.

6.4 Concomitant Medications/Therapies

Concomitant medications will be listed.

Version 2.0 6/30/2021 Page 8 of 13

Medications used for hemodialysis or during dialysis treatments will be summarized and listed separately for concomitant medications.

6.5 Treatment Compliance

N/A

6.6 Analysis of Primary Endpoint

The frequency for subjects with possible successful heparin-free sessions (0, 1, 2, or 3) will be displayed for each circuit. The descriptive statistics of subject's percent of successful heparin-free sessions will be presented for each dialysis circuits (A) and (B).

6.7 Analysis of Primary Safety Endpoint

Adverse events will be coded for system organ class and preferred term using Medical Dictionary for Regulatory Activities (MedDRA), Version 23.1. For all AEs and device related AEs, the number and percent of subjects with at least one occurrence, and the number of all occurrences under one preferred term, as well as under one system organ class, will be presented by circuit and % heparin.

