2. STUDY DESIGN

2.1. General Description

This is a randomized, open-label, cross-over study with subjects on thrice-weekly (in-center) hemodialysis. The study consists of a Screening Period, study Period 1, Washout Period, study Period 2, and a Follow-up Visit.

• Screening Period:

The Screening Period begins with signing of the informed consent form (ICF) and can extend up to 4 weeks in duration. After completing all required tests/procedures and determining/verifying the eligibility, the subject is randomly assigned to one of the circuit sequences, either AB or BA. The randomization is done in the electronic data capture (EDC) system.

Circuit A consists of the dialyzer with Endexo and CombiSet bloodline and Circuit B consists of the dialyzer with Endexo and Streamline bloodline.

• Period 1:

Period 1 consists of 5 HD sessions (Visits 1 to 5) on the dialyzer with Endexo with the CombiSet bloodline for sequence AB and Streamline bloodline for sequence BA according to the randomization, and different heparin doses shown below:

Visit 1: 100% of heparin as prescribed

Visit 2: 50% of heparin as prescribed

Visits 3, 4, 5: 0% of heparin

This period lasts for approximately two weeks per subject.

Version 2.0 6/30/2021 Page 3 of 13

Washout Period:

The Washout Period occurs between Period 1 and Period 2. It consists of three conventional HD sessions (Visits 6, 7, and 8). This period lasts approximately one week per subject.

• Period 2:

Period 2 consists of 5 HD sessions (Visits 9 to 13) on the dialyzer with Endexo with Streamline bloodline for sequence AB and CombiSet bloodline for sequence BA according to the randomization, and different heparin doses shown below:

Visit 9: 100% of heparin as prescribed,

Visit 10: 50% of heparin as prescribed,

Visits 11, 12, 13: 0% of heparin

• Follow-up Visit:

An in-center Follow-up Visit is to be conducted within 1 week of the subject's last scheduled study HD treatment. This visit cannot be combined with the last study HD visit.

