3.2. Changes in the Planned Analyses

Concurring with FDA's comments/suggestions, the secondary endpoint of adverse events, and device-related adverse events, became the primary safety endpoint.

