6.8 Analysis of Additional Assessments

These additional assessments will be analyzed under the analysis population.

- Distributions of clotting scores by circuit, by % heparin will be presented for dialyzer arterial end cap, venous end cap, venous chamber for each bloodline, arterial chamber for Combiset, and arterial pod and venous pod for Streamline.
- For HD delivered, arterial pressure, venous pressure, blood flow rate, dialysate flow rate, HD treatment duration, mean KECN, ultrafiltration volume, and blood volume process, descriptive statistics will be presented by circuit, and % heparin.
- For β_2 -microglobulin, the removal rate {((pre-HD post-HD)/pre-HD) x 100} will be calculated. Descriptive statistics will be presented by circuit, and % heparin for the pre-HD, post-HD and corrected post-HD β_2 -microglobulin concentrations, as well as removal rates from post-HD and corrected post-HD.
- For total volume of saline administered, descriptive statistics will be presented by circuit, and % heparin. Total volume for treating clotting, total volume for treating intradialytic symptoms, and total volume for medication delivery will be presented in the same manner. In addition, the total number of saline flushes and the total number of HD sessions received by subjects will be presented by circuit and % heparin for treating clotting, treating intradialytic symptoms, and for medication delivery.

Version 2.0 6/30/2021 Page 9 of 13

• For URR and spKt/V, descriptive statistics will be presented by circuit, and % heparin.

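### The primary safety table sets one session each at 100% and 50% heparin against three at 0% with no session denominator, so its heparin columns are not comparable

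*SAP*

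**What the plan says.** SAP 2.1 fixes the heparin schedule within each circuit period: "Visit 1: 100% of heparin as prescribed", "Visit 2: 50% of heparin as prescribed" and "Visits 3, 4, 5: 0% of heparin". Period 2 repeats the pattern, ending with "Visits 11, 12, 13: 0% of heparin". The protocol synopsis gives the same schedule.

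SAP 3.2 records that adverse events and device-related adverse events "became the primary safety endpoint". SAP 6.7 reports, for each preferred term and system organ class, "the number and percent of subjects with at least one occurrence" and the number of occurrences. These "will be presented by circuit and % heparin". The three heparin-free sessions therefore share one column, and no session count, rate or split by visit is specified. The default in SAP 5.1 of averaging within subject first does not apply, because 6.7 specifies its own statistic.

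The SAP mentions a session total elsewhere. For saline, SAP 6.8 presents "the total number of saline flushes and the total number of HD sessions received by subjects" by circuit and heparin level.

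**The concern.** The protocol's statistical methods planned adverse events for each circuit; the SAP added the split by heparin level. In a study of heparin-free dialysis, adjacent columns for 100%, 50% and 0% heparin will be read against one another. The 0% column collects events over three sessions and the others over one, so it would show more events and more affected subjects even if removing heparin changed nothing.

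The error can run in two directions. A reader may see a safety signal that is only extra exposure, or may dismiss a real excess as the product of more sessions. The distortion makes heparin-free dialysis look worse, so it does not flatter the device.

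**Working it through.** **Inputs.** Sessions per subject per circuit are 1, 1 and 3 at 100%, 50% and 0% heparin (SAP 2.1). SAP 2.4 plans 12 to 16 subjects. Neither document gives an adverse event rate, so the per-session probability p of an event is an assumption and is varied.

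**The plan's own figure.** SAP 2.4 states 36 to 48 heparin-free sessions per circuit. 12 × 3 = 36 and 16 × 3 = 48, so it reproduces. The same subjects give only 12 to 16 sessions per circuit at 100%, and again at 50%.

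**Event counts.** With the same expected number of events per session at every level and all sessions delivered, the expected count at 0% is 3 times that at 100% or 50%.

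**Percent of subjects with at least one event.** With independent sessions this is p for one session and 1 − (1 − p)³ for three. The ratio is 3 − 3p + p².

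| Assumed p | 100% or 50% column | 0% column | Ratio |
|---|---|---|---|
| 0.01 | 1.0% | 3.0% | 2.97 |
| 0.05 | 5.0% | 14.3% | 2.85 |
| 0.10 | 10.0% | 27.1% | 2.71 |
| 0.20 | 20.0% | 48.8% | 2.44 |
| 0.30 | 30.0% | 65.7% | 2.19 |
| 0.50 | 50.0% | 87.5% | 1.75 |

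Setting 3 − 3p + p² = 2.4 gives p ≈ 0.215, so the range of 2.4 to 3 holds for p up to about 20%.

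**Within-subject clustering.** Take a beta-binomial model with intraclass correlation ρ, s = 1/ρ − 1 and b = (1 − p)s. The chance of no event in three sessions is b(b+1)(b+2) / [s(s+1)(s+2)]. For p from 0.02 to 0.20 the ratio falls from 2.67 to 2.26 at ρ = 0.1, from 2.21 to 1.93 at ρ = 0.3, and from 1.81 to 1.64 at ρ = 0.5.

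**Early stopping.** Under SAP 3.1, a clotting score of 4 leads to withdrawal or a move to washout. Suppose each 0% session carries a chance w of being the subject's last in that block, independent of adverse events. Mean sessions are 1 + (1 − w) + (1 − w)². With w = 0.10 this is 1 + 0.90 + 0.81 = 2.71, which is also the expected count ratio. The subject-percent ratio is then 2.68 to 2.24 for p from 0.01 to 0.20. With w = 0.20 it is 2.42 to 2.05. Rare stopping changes little: w = 0.02 gives 2.91 to 2.40.

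The ratio stayed above 1 in every scenario.

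**Can the table mislead on direction?** Yes. If per-session risk at 0% were half that at 100% (2.5% against 5%), the expected percents would be 1 − 0.975³ = 7.3% at 0% and 5.0% at 100%. The safer level would look worse.

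**After the fix.** With p = 0.10, at most one event per session and 12 subjects, expected events over sessions are 1.2/12, 1.2/12 and 3.6/36. Each is 10 per 100 sessions, a ratio of 1.0.

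**The case against.** The strongest reply is that no comparison of adverse events between heparin levels is planned. The secondary objective (SAP 1.2) is to summarize events with both circuits. The only comparisons that SAP 5.2 mentions are between Circuits A and B, where adequate, and at a given heparin level those have equal planned exposure. No test, sample size or threshold rests on the 6.7 table. All of this stands and limits the consequence.

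A second reply is that nothing is lost. The 1:1:3 schedule is stated in both documents, 6.7 already gives occurrence counts, and SAP 5.1 lists all data. A reader could divide. This stands in part: rates can be rebuilt from the listings. Dividing by three is unreliable, however, because the rules in SAP 3.1 differ by circuit and period and can shorten the 0% block unevenly. Delivered sessions are the right divisor, and 6.7 does not show them.

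A third reply concerns the remedy. The saline sentence in SAP 6.8 could mean sessions with a flush for each reason rather than all sessions delivered. Section 6.8 also uses the analysis population, while safety uses the safety population (SAP 6.9), so the saline counts may not transfer. In addition, events are captured continuously from consent to completion or withdrawal (protocol synopsis, safety monitoring), and no rule ties an event between sessions to a heparin level. Both points stand, and the fix has to cover them.

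Two stronger readings are tempting. One is that the 0% column will look 2.4 to 3 times worse whatever happens. The documents do not support that: they give no event rate, and the range depends on low per-session risk, independence and full delivery. The other is that a real excess could never be separated from exposure. The counts and listings allow it, though the planned table does not.

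**Conclusion.** The point holds as a defect of presentation in the primary safety table. As planned, the heparin columns within a circuit are not comparable. Under equal per-session risk, expected counts at 0% are 3 times those at 100% or 50% if all sessions are delivered. The percent of subjects affected is about 2.4 to 3 times higher for independent sessions with p up to about 20%, and roughly 1.6 to 2.7 times higher with clustering, higher risk or stopping at 10% to 20% per session. The values of p, ρ and w are all assumptions. The 1:1:3 schedule and the missing denominator come from the documents. The change is worth making because it is cheap and concerns the primary safety endpoint, but no inference in the plan fails without it.

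**What to change.** In SAP 6.7, add to each circuit-by-heparin cell:

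- the number of HD sessions actually delivered, counted in the safety population;
- adverse events per 100 sessions delivered;
- the number and percent of sessions with at least one adverse event.

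Add one attribution rule: assign each event by onset to the most recent study session, and show washout and follow-up events separately. The rule should state where the windows after Visits 5 and 13 end. It should also place events before Visit 1, which have no preceding session, outside the heparin columns.

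State that any descriptive reading across heparin levels uses the per-session figures. Add a note that heparin level follows a fixed visit order (100%, 50%, then 0%), so even these rates cannot separate heparin level from order. Keep the subject counts as supporting rows.

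The cost is a few table rows and one rule in the SAP. No new data are needed.

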6.8 Analysis of Additional Assessments

These additional assessments will be analyzed under the analysis population.

- Distributions of clotting scores by circuit, by % heparin will be presented for dialyzer arterial end cap, venous end cap, venous chamber for each bloodline, arterial chamber for Combiset, and arterial pod and venous pod for Streamline.
- For HD delivered, arterial pressure, venous pressure, blood flow rate, dialysate flow rate, HD treatment duration, mean KECN, ultrafiltration volume, and blood volume process, descriptive statistics will be presented by circuit, and % heparin.
- For β_2 -microglobulin, the removal rate {((pre-HD post-HD)/pre-HD) x 100} will be calculated. Descriptive statistics will be presented by circuit, and % heparin for the pre-HD, post-HD and corrected post-HD β_2 -microglobulin concentrations, as well as removal rates from post-HD and corrected post-HD.
- For total volume of saline administered, descriptive statistics will be presented by circuit, and % heparin. Total volume for treating clotting, total volume for treating intradialytic symptoms, and total volume for medication delivery will be presented in the same manner. In addition, the total number of saline flushes and the total number of HD sessions received by subjects will be presented by circuit and % heparin for treating clotting, treating intradialytic symptoms, and for medication delivery.

Version 2.0 6/30/2021 Page 9 of 13

• For URR and spKt/V, descriptive statistics will be presented by circuit, and % heparin.

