Exploratory Assessment	Pictures of the arterial and venous end caps of the dialyzer with Endexo, arterial and venous drip chambers for CombiSet bloodline and venous chambers, arterial and venous pods for Streamline bloodline will be taken by the study sites at the end of each HD session.				
	The data listed below will be collected in the study:				
	1. Demographics				
	2. Medical History, historical laboratory values and Concomitant Medications				
	3. Physical Exam, Vital Signs, Body Measurements (height, weight)				
	4. Adverse events, serious adverse events, and device deficiencies				
	5. HD Treatment parameters:				
	a. Initial HD Prescription				
	b. Data collection during dialysis treatment:				
	 Blood flow rate (Qb), dialysate flow rate (Qd), arterial pressure (AP), venous pressure (VP), at initiation of the HD sessions and every 30±15 minutes 				
	 KECN recorded at initiation of the HD sessions and every 30±15 minutes 				
	c. HD Treatment Data:				
	 Treatment Time (Td), mean Qb, mean Qd, mean AP and VP, mean ultrafiltration volume and rate, and blood volume processed 				
Data Collection	 Mean KECN 				
	d. Volume, time and the reason for saline flushes administration (other than for circuit priming or rinse back)				
	e. HD Treatment-related Medications (total heparin units given [bolus + maintenance]) when applicable				
	f. Duration of blood flow cessation during hemodialysis treatment estimated as the difference between the Ultrafiltration (UF) clock and the Remaining Time on Dialysis (RTD) clock.				
	6. Thrombus scoring at the end of each HD session:				
	a. Visual thrombus scoring of dialyzer end caps, and bloodline drip chambers and pods will be performed (Grade 1–4) and recorded by site staff (the investigator or a designee). For further details, see Appendix II.				
	b. Digital pictures of the dialyzer end caps, and bloodline drip chambers and pods will be taken by site staff.				
	7. Laboratory Assessments:				
	a. At screening:				
	 Serum pregnancy test for females of childbearing potential 				

	b. Periods 1 and 2:
	 Pre- and post-hemodialysis for Visits (1–5) and (9–13):
	 Complete Blood Count with differential (CBC with diff), Blood Urea Nitrogen (BUN), and Albumin
	 Pre- and post-hemodialysis for Visits 1,3, 9 and 11:
	 β₂ Microglobulin (B2M), C-Reactive Protein (CRP), Interleukin-6 (IL-6) and Ferritin

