2.4. Determination of Sample Size

Version 2.0 6/30/2021 Page 4 of 13

A sample size was not calculated. A total of 12 to 16 subjects with three heparin free HD treatments for each circuit for each subject or 36 to 48 HD sessions per circuit was considered appropriate for a feasibility study.

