5.2 Analysis Methods for Endpoints

If adequate, 95% confidence interval will be calculated for each dialysis circuits (A) and (B). For comparisons, if adequate, paired-t tests may be performed between dialysis circuits (A) and (B) for continuous endpoints, McNemar's tests may be employed for categorical endpoints.

For 0% heparin, the average of a continuous endpoint from multiple HD treatments will be calculated for each subject, then descriptive statistics will be summarized at subject level.

For β_2 -microglobulin, the laboratory results for post dialysis will be corrected for ultrafiltration using the formula in Bergström and Wehle (1987).

Uncorrected value Corrected value = -----,
$$1 + \Delta W/(0.2PW)$$

Version 2.0 6/30/2021 Page 6 of 13

where ΔW = pre-dialysis weight – post dialysis weight, PW is the post dialysis weight.

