6.9.2 Clinical Laboratory Evaluation

Descriptive statistics for each test, and changes (absolute and relative from post-HD to pre-HD will be presented by circuit and % heparin for hematology and for serum chemistry. In addition, descriptive statistics of changes of pre-HD of 50% heparin session and pre-HD of all 0% heparin sessions from baseline, which is defined as the pre-HD tests of 100% heparin session, will be presented.

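### SAP 6.8 summarises dialysis performance separately at each heparin level and plans no within-subject change from the 100% session

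*SAP*

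**What the plan says.** SAP 2.1 fixes the heparin order in each period: 100% at the first session, 50% at the second, then none ("Visits 3, 4, 5: 0% of heparin"; likewise Visits 11 to 13 in Period 2). The circuit does not change within a period.

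SAP 6.8 reports the performance measures by column. For adequacy: "For URR and spKt/V, descriptive statistics will be presented by circuit, and % heparin". For delivered treatment, including mean KECN: "ultrafiltration volume, and blood volume process, descriptive statistics will be presented by circuit, and % heparin". The B2M removal rate is handled in the same way. The protocol synopsis (Data Collection, Laboratory Assessments) schedules B2M at "Pre- and post-hemodialysis for Visits 1,3, 9 and 11", which gives one 100% and one 0% session per circuit.

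SAP 5.2 averages the 0% sessions within subject. The one comparison it names for continuous endpoints is between circuits: "For comparisons, if adequate, paired-t tests may be performed between dialysis circuits (A) and (B) for continuous endpoints". Its confidence intervals are optional and are per circuit.

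SAP 6.9.2 does use the 100% session as a baseline, but for pre-dialysis laboratory tests: "changes of pre-HD of 50% heparin session and pre-HD of all 0% heparin sessions from baseline".

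**The concern.** Each subject is his or her own reference for performance with heparin, on the same dialyzer and bloodline and a few sessions earlier. The plan collects that reference but never sets it against the heparin-free sessions for the measures that would show lost dialyzer function.

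Two things are lost. First, the spread of individual changes and the precision of the mean change depend on the within-subject correlation, and column means and SDs do not contain it. Prescribed session lengths run from 180 to 270 minutes (protocol, Inclusion Criteria), so subjects may differ widely from one another, and column SDs then reflect mostly that difference.

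Second, the columns need not contain the same people. The analysis population (SAP 5.3) requires only one heparin-reduction treatment, which a 50% session appears to satisfy. Under SAP 3.1, complete clotting of the CombiSet line in Period 1 sends the subject to washout, and the other complete-clotting cases lead to withdrawal. A subject whose line clots completely at Visit 2 can therefore be in the 100% column for that circuit with no 0% data. SAP 5.5 imputes nothing.

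**Working it through.** **The plan's own figure.** SAP 2.4 states "A total of 12 to 16 subjects with three heparin free HD treatments for each circuit for each subject or 36 to 48 HD sessions". These counts apply to each circuit: 12 × 3 = 36 and 16 × 3 = 48, so the figure reproduces. The same section says "A sample size was not calculated", so there is no SD, power or effect size to work from. All SDs and correlations below are assumptions.

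**Point estimate.** The 0% sessions are averaged per subject first (SAP 5.1, 5.2). If every subject has both levels, the mean of the 0% column minus the mean of the 100% column equals the mean within-subject difference. The columns therefore lack the SD and interval of that difference, not the difference itself.

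**Precision for spKt/V, n = 12.** Assume within-subject (session-to-session) SD sw = 0.10, between-subject SD sb = 0.15 to 0.30, one 100% session, the mean of three 0% sessions, and a change that is the same in all subjects apart from session noise.

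- Paired SE = √[(sw² + sw²/3)/12] = √(0.01333/12) = 0.033. Half-width with t on 11 df: 2.20 × 0.033 = 0.07.
- Columns treated as independent: SE = √[(2sb² + sw² + sw²/3)/12].
  - sb = 0.15: √(0.05833/12) = 0.070; half-width 1.96 × 0.070 = 0.14.
  - sb = 0.30: √(0.19333/12) = 0.127; half-width 1.96 × 0.127 = 0.25.

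The SE ratio is 0.033/0.070 to 0.033/0.127, a reduction of 52% to 74%. Using t on 22 df (2.07) for the columns gives 0.14 and 0.26, so the choice of multiplier hardly matters.

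**Free of units, and for B2M.** Let ρ be the within-subject correlation and k the number of 0% sessions averaged. In units of the single-session SD, the variance of one paired difference is (1 − ρ)(1 + 1/k), and the independent-columns counterpart is 1 + ρ + (1 − ρ)/k. Each is divided by n. The 95% half-widths use t on n − 1 and 2n − 2 df:

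| Measure | n | Paired, ρ = 0.5 / 0.8 / 0.9 | Columns as independent |
|---|---|---|---|
| k = 3 (e.g. spKt/V, URR, blood volume) | 12 | 0.519 / 0.328 / 0.232 | 0.773 / 0.818 / 0.832 |
| k = 3 | 16 | 0.435 / 0.275 / 0.195 | 0.659 / 0.698 / 0.710 |
| k = 1 (B2M) | 12 | 0.635 / 0.402 / 0.284 | 0.847 at each ρ |
| k = 1 (B2M) | 16 | 0.533 / 0.337 / 0.238 | 0.722 at each ρ |

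The independent-columns interval is 1.33 to 3.65 times as wide. The spKt/V figures above cannot be carried over to B2M, which has a single 0% session per circuit.

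**Different subjects in the two columns.** Suppose removing heparin changes nothing, but m of n subjects have no 0% data and their mean differs from the rest by d SDs. The column means then differ by (m/n)d. With 2 of 12 and d = 1 this is 0.17 SD; with 3 of 12 it is 0.25 SD; with 1 of 16 and d = 0.5 it is 0.03 SD. These m and d are illustrations.

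**The case against.** The strongest reply is that this is not the study's question. The objective is to explore the feasibility of heparin-free dialysis. The primary endpoint judges each heparin-free session against absolute criteria, including spKt/V of at least 1.2, and no objective asks for a heparin effect. The measures here are additional assessments, for which the protocol promised only descriptive statistics per circuit; splitting them by heparin level already goes further. This stands, and it limits the point to a secondary summary. But a within-subject mean, SD and interval is itself descriptive, and 6.9.2 shows that the SAP accepts this kind of contrast.

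A reader might infer that the effect of removing heparin goes wholly unestimated, or that the only within-subject contrast anywhere is circuit A against B. The documents support neither reading. With complete data the mean difference is visible in the columns, SAP 5.1 promises listings of all data, and 6.9.2 plans changes from the 100% session for laboratory values. Nor would the paired difference isolate heparin: the order is fixed, so visit order goes with it.

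It is also fair to say that the SAP plans no independent-columns interval. The width comparison measures what a reader loses by treating the columns as separate samples, not a defect in a planned test.

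On differing subjects, the analysis population leaves out anyone who stops before any heparin reduction, and n is reported for each column. That narrows the problem without removing it. Pairing has its own selection: it drops subjects with no 0% session and rests on fewer sessions for those stopped early. With one 0% session instead of three, a subject's difference has variance 2sw² rather than (4/3)sw². This objection stands, and the fix has to disclose it.

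**Conclusion.** The point holds as a modest, inexpensive improvement to SAP 6.8. For spKt/V, URR, corrected B2M removal rate, mean KECN and blood volume processed, no within-subject change between heparin levels is planned. The SD and confidence interval of that change cannot be recovered from the planned tables, and after early stopping even the difference in means can be distorted.

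The size is hypothetical. The half-widths for spKt/V (about 0.07 against 0.14 to 0.25 at n = 12) depend on the assumed SDs and on a change that is similar across subjects. If the change varies between subjects, the paired interval widens, and that variation is also hidden in the columns. The primary endpoint analysis is not affected, and the change should not be described as a pure heparin effect.

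**What to change.** Add one paragraph and one table to SAP 6.8, marked exploratory, using data already collected. For each circuit, define the within-subject change as the mean of the available 0% sessions minus the 100% session of the same period, for spKt/V, URR, mean KECN and blood volume processed. For corrected B2M removal rate, use the single 0% session minus the single 100% session. Report the number of pairs, mean, SD and 95% CI. Also report how many subjects have no pair or, where three 0% sessions are scheduled, fewer than three, with reasons.

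Footnote two limits: the change carries visit order, because heparin always falls from 100% to 50% to 0%; and subjects stopped for clotting contribute fewer or no 0% sessions, so the summary may understate a loss of performance. Keep the planned columns beside it.

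The cost is the extra text and programming. The remaining risk is that a narrow interval is over-read as a heparin effect, which the label and footnote should guard against.
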